Official Title: Management of Spontaneous Ruptured Hepatocellular Carcinoma

- Partial Hepatectomy and Prognosis: A Retrospective Study

NCT number: Not available

Date of the document: 05/03/2018

Statistical analysis plan

All of the analyses were carried out using SPSS 24.0 (IBM), and a two-sided $P < 0.05$ was considered statistically significant.

1. A comparison of the clinicopathologic characteristics of all the patients between the partial hepatectomy group and the non-surgical treatment group before propensity score matching (PSM): there are (or no) significances for patients' characteristics before PSM.

The variables are: age, sex, HBs-Ag (+), HCV-Ab, tumor size, tumor number, macroscopic vascular invasion (MVI), cirrhosis, portal hypertension, Child-Pugh grade, hemorrhagic shock, hemoglobin, red blood cell (RBC), transfusion during hospitalization, a-fetoprotein (AFP), aspartate aminotransferase (AST), albumin, total bilirubin, Barcelona Clinic Liver Cancer (BCLC) stage, sorafenib, 30-day mortality.

Statistical analysis method: Pearson's χ^2 test, χ^2 test with Yates' correction, Fisher's exact test, Wilcoxon's rank-sum test and Student's t test.

2. Univariate and multivariate analysis of the predictive factors associated with overall survival (OS) before PSM: surgery or non-surgical treatment is (or not) an independent risk factor of overall survival.

The variables included are: age, sex, tumor size, tumor number, MVI, cirrhosis, portal hypertension, treatment, hemorrhagic shock, distant metastasis, AST, AFP, platelet, hemoglobin, sorafenib, Child-Pugh grade.

Statistical analysis method: univariate analysis was performed using the Kaplan-Meier method compared by the log-rank test; multivariate analysis was performed using the COX regression model.

3. A comparison of the clinicopathologic characteristics of all of the patients between the partial hepatectomy group and the non-surgical treatment group after PSM: there is no significance for patients' characteristics after PSM.

The variables included in PSM are: age, sex, tumor size, tumor number, MVI, cirrhosis, portal hypertension, hemorrhagic shock, hemoglobin, red blood cell (RBC), transfusion during hospitalization, a-fetoprotein (AFP), aspartate aminotransferase (AST), albumin, total bilirubin.

Statistical analysis method: PSM, a caliper of 0.5, 0.3, 0.2, 0.1, 0.05, 0.02, 0.01 would be used.

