4. Univariate and multivariate analysis of the predictive factors associated with OS after PSM: surgery or non-surgical treatment is (or not) an independent risk factor of overall survival.

The variables included are: age, sex, tumor size, tumor number, MVI, cirrhosis, portal hypertension, treatment, hemorrhagic shock, distant metastasis, AST, AFP, platelet, hemoglobin, Sorafenib, Child-Pugh grade.

Statistical analysis method: univariate analysis was performed using the Kaplan-Meier method compared by the log-rank test; multivariate analysis was performed using the

COX regression model.

5. Comparison of OS and recurrence-free survival (RFS) between the emergency partial hepatectomy group and the staged partial hepatectomy group.

Statistical analysis method: univariate analysis was performed using the Kaplan-Meier method compared by the log-rank test.

6. Comparison of OS and RFS between the staged early partial hepatectomy group and the staged late partial hepatectomy group.

Statistical analysis method: univariate analysis was performed using the Kaplan-Meier method compared by the log-rank test.

7. Difference in 30-day mortality of peritoneal dissemination between the groups at different times.

Statistical analysis method: Pearson's χ^2 test, χ^2 test with Yates' correction and Fisher's exact test.

8. Univariate and multivariate logistic regression analysis of postoperative peritoneal dissemination.

The variables included are: age, sex, tumor size, tumor number, MVI, cirrhosis, estimated intraperitoneal bleeding, Child-Pugh grade, tumor differentiation, resection margin, type of hepatectomy, timing of hepatectomy.

Statistical analysis method: univariate and multivariate logistic regression analysis.

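### Items 2 and 4 test OS with treatment as a fixed covariate although resections include staged operations; on the likelier grouping and two plausible time origins this is biased towards surgery, and matching does not remove it

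*SAP*

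**What the plan says.** Item 1 compares patients' characteristics "between the partial hepatectomy group and the non-surgical treatment group before propensity score matching (PSM"), so the two groups are named by treatment. Item 2 then asks whether "surgery or non-surgical treatment is (or not) an independent risk factor of overall survival" and puts treatment in a list of ordinary covariates: "The variables included are: age, sex, tumor size, tumor number, MVI, cirrhosis, portal hypertension, treatment, hemorrhagic shock". The method is "univariate analysis was performed using the Kaplan-Meier method compared by the log-rank test; multivariate analysis was performed using the COX regression model". Item 4 repeats the question, the covariates and the methods in the matched set.

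Item 5 is headed "Comparison of OS and recurrence-free survival (RFS) between the emergency partial hepatectomy group and the staged partial hepatectomy group" and item 6 "Comparison of OS and RFS between the staged early partial hepatectomy group and the staged late partial hepatectomy group". Item 8 models the timing of resection together with margin and hepatectomy type. The matching list in item 3 begins "The variables included in PSM are: age, sex, tumor size, tumor number, MVI" and continues with clinical and laboratory variables. None of them records survival to an operation.

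The SAP does not give the OS time origin, the group of a patient who dies before a planned staged operation, or the eligibility of early deaths. The protocol may give them, and their absence here is not the point. The point is the stated method, set against the delayed operations that the same document describes.

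**The concern.** A log-rank test or a fixed Cox term by treatment takes group membership as known at time zero. For a staged resection it is not: the patient joins the surgical group only by surviving to the operation.

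Treatment received is the likelier grouping rule. The study is retrospective and its groups are named by treatment. Recurrence-free survival by timing group, resection margin and hepatectomy type exist only in patients who were resected. On that rule, a staged candidate who dies waiting counts as non-surgical. With OS from rupture or admission, the surgical group is credited with a wait during which none of its members could die, and the other group takes the waiting deaths. Starting the clock at operation in surgical patients only removes the first effect, not the second.

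Items 2 and 4 appear to carry the study's main comparison. Under these conditions an OS advantage could not be separated from having lived to be operated on, and agreement between the unmatched and matched results would be false reassurance.

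**Working it through.** **Inputs.** From the SAP: two-sided significance at 0.05, treatment as an ordinary covariate, and staged resections. It gives no sample size, event count, emergency share, waiting time or early mortality. There is therefore no figure of its own to reproduce, and every numerical input below is assumed.

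**Step 1: the mechanism by hand.** Take 200 patients: 20% emergency resection (40), 40% planned for staged resection (80), the other 80 non-surgical. Let 19% die within 30 days whatever the treatment and, for simplicity, let every staged operation fall on day 30.

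- Grouped by intention: 120 × 0.19 = 22.8 deaths and 80 × 0.19 = 15.2 deaths, 19% in each group.
- Grouped by treatment received: 80 × 0.19 = 15.2 staged candidates die first and move across. Surgical: 40 + 64.8 = 104.8 patients, 40 × 0.19 = 7.6 deaths, 7.3%. Non-surgical: 80 + 15.2 = 95.2 patients, 15.2 + 15.2 = 30.4 deaths, 31.9%.

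Treatment does nothing here, yet the groups differ widely. Starting the clock at operation leaves the 15.2 moved deaths where they are. So does covariate matching, because what put these patients in the other group is the death itself. Putting all staged operations on one late day exaggerates the effect; spread delays give less.

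**Step 2: simulation with spread delays, true HR 1.** N = 200, 300 replicates per scenario. One binary severity covariate is adjusted for, and matched exactly 1:1 in place of PSM. Intention to operate averages 60%; later median OS is 10 months. 30-day mortality is about 7% (constant hazard: 1 − 0.5^(1/10) = 0.067), 15% or 30%. Emergency share of intended resections is 70% or 30%. Staged day is uniform from 0.25 to 1 or 2 months. Deaths while waiting are labelled non-surgical. The nominal rate of a false finding for surgery is 0.05/2 = 2.5%. Three of the 12 scenarios:

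| 30-day mortality; emergency share; window end | HR from rupture, before / after matching | HR from operation in surgical patients only, before / after | False finding for surgery (rupture origin), before / after | Time-dependent Cox HR |
|---|---|---|---|---|
| 7%; 70%; 1 month | 0.97 / 0.97 | 0.98 / 0.98 | 4.7% / 3.7% | 1.00 |
| 15%; 30%; 2 months | 0.76 / 0.76 | 0.81 / 0.82 | 41% / 30% | 1.00 |
| 30%; 30%; 2 months | 0.62 / 0.61 | 0.66 / 0.66 | 86% / 73% | 0.99 |

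Over all 12, time-dependent Cox gave 0.98–1.01 with 3.0–6.0% two-sided rejection, and a landmark at the end of the window 0.98–1.02 with 3.0–6.3%. Simulation error is √(0.05 × 0.95/300) = 1.3 points. A second simulation (18 settings, two covariates, 60,000 patients each, adjusted Cox) gave fixed-label HRs of 0.61–0.96 from admission and 0.65–0.98 from the mixed origin.

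**Step 3: readings under which the bias goes or turns.** In the same 18 null settings:

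- groups by intended treatment: 0.99–1.02;
- cohort alive past the whole surgery window: 0.98–1.03;
- each group from its own treatment start, waiting deaths excluded: 1.00–1.20 if non-surgical treatment is as delayed as staged surgery, 0.82–1.00 if it starts on day 0–1.

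**Step 4: operative mortality.** With an assumed 10% operative mortality, time-dependent Cox gave 1.14–1.23. The landmark gave only 1.02–1.09, because 73–91% of operative deaths fell before it. The fixed-label HR was 0.70–1.09.

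**The case against.** The strongest objection is that Kaplan-Meier, log-rank and Cox are not wrong in themselves. They fail here only under a grouping rule, a time origin and an eligibility rule that the SAP leaves open and the protocol may settle. Items 5, 6 and 8 show that the timing subgroups were resected, not where a patient who died waiting was placed; such patients may have been excluded. The simulated sizes run from negligible to overwhelming and carry no information from the document. The simulations also assume the disputed grouping rule, so they cannot confirm it.

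All of that stands as a limit on the claim, and is why the point is conditional. It does not dispose of it: the choice of method belongs in an SAP, and the method named has no safeguard for a delayed exposure that the SAP itself describes.

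A reader might infer more, in three ways that the document does not support.

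- That early deaths are certainly in the cohort, because the item 1 list ends with "Barcelona Clinic Liver Cancer (BCLC) stage, sorafenib, 30-day mortality". No origin is given for that mortality, and item 7 uses a 30-day mortality between timing groups, so it may run from treatment.
- That the reported HR will favour surgery. Step 4 shows that operative mortality can bring the net HR to 1 or above.
- That a landmark analysis settles the matter. It discards most early operative deaths, which are part of the effect of surgery, and so can itself favour surgery.

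**Conclusion.** The concern holds in conditional form and should be fixed. With groups by treatment received, and OS from rupture or admission or from operation in surgical patients only, items 2 and 4 are biased towards surgery, and the item 3 covariates do not remove this. The bias is absent under intended-treatment groups or a cohort alive past the whole surgery window. Its direction is undetermined if each group starts at its own treatment.

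The size is unknown. It is negligible with mostly emergency surgery and few early deaths, and large with many staged operations, long waits and high early mortality. The simulated HRs show what assumed inputs produce; they do not estimate this study's bias. Confidence is moderate, because it rests on the likelier reading of the groups, not on a stated rule.

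**What to change.** - **Origin.** Count OS from one common origin, rupture or admission, in all patients.
- **Item 2.** Make the main treatment analysis a Cox model with hepatectomy as a time-dependent covariate: 0 before operation, 1 after.
- **Item 4.** Match each operated patient, on the propensity score, to a patient still alive and not yet operated on at that number of days from the origin. Follow both from that day. Handle controls operated on later by a rule fixed in advance, for example time-dependent treatment. Operative deaths then stay in the analysis.
- **Sensitivity only.** Use landmark Kaplan-Meier, and PSM among landmark survivors, with the landmark day written down in advance. State that they drop operative deaths before the landmark and so can favour surgery.
- **Descriptive only.** Keep the fixed-group comparison.

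The cost is SAP wording and modest extra analysis. Day-level operation dates are needed; items 5, 6 and 8 show that timing groups exist, not that such dates are held. Pairs may be lost. For the landmark sensitivity analysis at n = 200, the 18 assumed settings dropped 5–39% of patients and left 39–67 pairs, against 61–72 under fixed-label matching. The matching proposed for item 4 was not simulated, so its yield of pairs is unknown.

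Unmeasured selection for surgery remains. With one unmeasured prognostic factor added to the null simulation, time-dependent and landmark Cox still gave 0.89–0.93, against 0.56–0.87 for the fixed label from admission.

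### Log-rank as the only univariate method for overall survival forces six measured variables into groups with no fixed cut-points; the coding of these variables in the Cox models is left open

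*SAP*

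**What the plan says.** Item 2 (OS before propensity score matching, PSM) and item 4 (OS after matching) use the same two-step method. For the first step, "univariate analysis was performed using the Kaplan-Meier method compared by the log-rank test". For the second, "multivariate analysis was performed using the COX regression model". No other univariate method is named for OS.

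One list of 16 factors serves both steps. In item 2 it begins "age, sex, tumor size, tumor number, MVI, cirrhosis, portal hypertension, treatment, hemorrhagic shock, distant metastasis" and ends "AST, AFP, platelet, hemoglobin, sorafenib, Child-Pugh grade". Item 4 repeats it, ending "AST, AFP, platelet, hemoglobin, Sorafenib, Child-Pugh grade". Six entries are measured quantities: age, tumor size, AST, AFP, platelet and hemoglobin.

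The SAP gives no cut-points for these six and no rule for choosing them. It does not say whether they enter the Cox models as continuous terms or as categories. Both items are meant to decide whether surgery is independently associated with OS. The significance rule is "a two-sided $P < 0.05$ was considered statistically significant".

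**The concern.** A log-rank test cannot be applied to a measured variable until it has been cut into groups. The named method therefore decides that all six will be grouped in the univariate step, and leaves the cut-points to be chosen with the data in hand. When risk changes smoothly with the variable, grouping discards information, and a retrospective series cannot simply recruit more patients to recover it.

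The second consequence is conditional. Because one list serves both steps, an analyst could well carry the groups into the Cox model. In item 2 that model is the only adjustment for differences between operated and non-operated patients. Within a coarse group, patients selected for surgery can still differ in prognosis from those who were not, and that difference would be credited to surgery.

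Other parts of the SAP use methods that accept measured values: item 1 lists the t and rank-sum tests, and item 8 uses univariate logistic regression. Items 5 and 6 apply the log-rank test to natural treatment groups and are not affected.

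**Working it through.** The SAP gives no sample size, event count, effect size or power, so there is no figure of its own to reproduce. The two-sided 5% level, the variable lists and the methods come from the SAP. Everything else below is an assumption.

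**Step 1. Information kept by a two-group split.** For a normally distributed covariate with a log-linear effect, split at quantile q, the efficiency relative to the continuous term is φ(z_q)² / [q(1 − q)]. At the median this is 0.3989² / 0.25 = 0.637 (= 2/π).

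**Step 2. Power.** If the continuous term has 80% power, its expected z is 1.960 + 0.842 = 2.802. After a median split it is 2.802 × √0.637 = 2.235, and power is Φ(2.235 − 1.960) = Φ(0.275) ≈ 61%. The same formula gives:

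| Split | Efficiency | Power, from 80% | Power, from 90% |
|---|---|---|---|
| 50/50 | 0.64 | 61% | 73% |
| 30/70 | 0.58 | 57% | 69% |
| 20/80 | 0.49 | 50% | 62% |
| 10/90 | 0.34 | 37% | 48% |

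**Step 3. The same loss in events.** Assume an HR of 1.3 per SD. The continuous term needs 2.802² / (ln 1.3)² = 7.85 / 0.0688, about 115 events, for 80% power. The halves of a median split differ by 2 × 0.798 = 1.596 SD, a log HR of 1.596 × 0.262 = 0.419. Schoenfeld's formula then gives 4 × 7.85 / 0.419², about 180 events. A separate simulation (n = 200, log HR 0.22 per SD) agrees: power fell from 79% to 58%.

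**Step 4. Bias in item 2 if the groups enter the Cox model.** Assumptions: true treatment HR 1.00; 300 patients; six normal confounders, all favouring the treated group; treatment logit slopes of 0.2, 0.3 and 0.4 and log HRs of 0.15, 0.20 and 0.30 per SD (weak, moderate, strong). Each cell shows the estimated HR, with type I error in brackets where available.

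| Adjustment | Weak | Moderate | Strong |
|---|---|---|---|
| None | 0.86 | 0.76 | 0.61 |
| Median splits | 0.94 (7.8%) | 0.89 (12.7%) | 0.80 (32.4%) |
| Tertiles | 0.97 (6%) | 0.93 (7%) | 0.88 (14%) |
| Quartiles | 0.98 (8%) | 0.96 (6%) | 0.91 (10%) |

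Continuous terms gave HRs of 1.00 to 1.01 and type I error of 4.5% to 6.0% across the three scenarios. The main runs used 1,000 replicates, so a type I error near 5% has a Monte Carlo standard error of √(0.05 × 0.95 / 1000) ≈ 0.7 percentage points; small differences between cells mean little. A repeat of the median-split row gave the same HRs and type I errors of 8%, 11% and 29%.

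The share of log-scale bias left by median splits is ln 0.94 / ln 0.86 = 0.41, ln 0.89 / ln 0.76 = 0.42 and ln 0.80 / ln 0.61 = 0.45. A second simulation, with 4,000 patients per replicate and one, three or six confounders, left 33% to 43% after median splits and 49% to 61% after 80/20 splits.

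**Step 5. Item 4.** Age, tumor size, AST, AFP and hemoglobin are also in the PSM list of item 3; platelet is not. Matching on five of the six confounders as continuous terms within a 0.2-SD caliper (both assumptions), followed by a median-split Cox model, gave HRs of 0.99, 0.98 and 0.96 and type I errors of 5.5%, 4.3% and 6.6%.

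**The case against.** The strongest reply is that the SAP never says the Cox models use categories. That stands. The t and rank-sum tests in item 1 show that at least some variables are held as measured values, and with continuous Cox terms only the univariate power loss remains. A reader might infer from the shared list that the plan produces a biased surgery effect. The text does not support that: the coding is unstated, so the bias is a risk to close off.

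A reader might also take the log-rank step to be a screen that chooses covariates for the Cox model. Nothing in items 2 or 4 says so; the list is given for both steps. Treatment is itself categorical, so its own log-rank test loses nothing.

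The simulated bias is towards the unfavourable end. It uses median splits of all six variables, all favouring surgery, although the SAP states neither the number of groups nor the direction. It also leaves out the other Cox covariates, such as hemorrhagic shock, cirrhosis and Child-Pugh grade, which may carry some of the same information. Tertiles and quartiles reduce the bias, and matching largely removes it in item 4, although the coding in the propensity model is not stated either.

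Finally, it would be wrong to say that every cut-off is worse than a continuous term. With an assumed threshold effect in a skewed marker (n = 200, HR 1.65 above the cut), the correct cut had 83% power and the log-continuous term 59%.

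These points limit the size of the concern. They leave two facts in place: the named univariate method forces grouping, and neither cut-points nor Cox coding are fixed.

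**Conclusion.** The point holds in limited form. Items 2 and 4 force six measured variables into groups for the univariate OS tests, with no cut-points fixed. Under roughly log-linear effects, power falls from 80% to about 61% with a median split, more with an uneven two-way split and less with additional categories; a true threshold effect could reverse this.

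Bias in the surgery effect is conditional on the groups being carried into the unmatched Cox model of item 2. Its size rests on assumed confounding strength, and its direction on the assumption that operated patients have the better prognosis. Item 4 should be much less affected. The documents do not show that the planned surgery estimate is biased. Severity is minor to moderate, and the improvement is cheap.

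**What to change.** In items 2 and 4:

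- Use univariable Cox regression for age, tumor size, AST, AFP, platelet and hemoglobin.
- Enter the same six as continuous terms in the multivariable Cox models, with AFP log-transformed and restricted cubic splines or another flexible form where the relation is non-linear. State this coding in the SAP.
- Keep Kaplan-Meier and log-rank for the categorical factors. Use Kaplan-Meier curves for the continuous factors for display only, with cut-points fixed in advance.

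The cost is a change of wording and slightly more analysis work. Cox regression is already in the plan, so no new method is needed. Hazard ratios would be reported per unit or per doubling, which clinicians may find less familiar than a high-versus-low contrast.

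### Item 3 of the SAP judges balance after matching only by non-significance, which depends on the number of pairs, so a small match can easily pass with sizeable imbalance

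*SAP*

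**What the plan says.** The SAP's opening paragraph sets one threshold for everything: "a two-sided $P < 0.05$ was considered statistically significant".

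Item 1 compares the two treatment groups before matching and leaves the result open: "there are (or no) significances for patients' characteristics before PSM". The methods it names are all significance tests, ending with "Fisher's exact test, Wilcoxon's rank-sum test and Student's t test". Items 2 and 4 also leave their answers open.

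Item 3 makes the same comparison after matching, but states the result as settled: "there is no significance for patients' characteristics after PSM". Its method line names only the matching and a list of calipers ("a caliper of 0.5, 0.3, 0.2, 0.1, 0.05, 0.02, 0.01 would be used"). It names no balance measure and does not say what follows if a characteristic still differs.

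Item 4 takes the matched patients into the survival analysis. For the unadjusted part, "univariate analysis was performed using the Kaplan-Meier method compared by the log-rank test"; a multivariable Cox model follows.

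**The concern.** A P value mixes two things: how far apart the groups are, and how many patients are compared. Matching discards patients, so a characteristic can move from significant to non-significant partly because fewer patients remain. Non-significance after matching is therefore weak evidence that the groups have become alike.

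In a retrospective comparison of surgery with non-surgical treatment, the matching is what makes the comparison credible. If the factors that decide who is resected still differ, the matched log-rank comparison will attribute part of that difference to surgery. The SAP has no other measure that would show this to a reader.

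**Working it through.** **Inputs from the SAP.** The level is two-sided 0.05. Item 3 has 15 matching variables as punctuated, or 14 if red blood cell and transfusion are one item. The item 4 list has 16 entries including treatment. The SAP gives no number of pairs, so there is no figure of its own to reproduce.

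**Assumptions.** n = 30, 50, 100 and 200 pairs. Tests are treated as unpaired, like those named in item 1; item 3 names none of its own.

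**Step 1: largest observed standardized difference that stays non-significant.** Formula: t(0.975, 2n−2) × √(2/n).

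- n = 30: 2.002 × 0.258 = 0.52
- n = 50: 1.984 × 0.200 = 0.40
- n = 100: 1.972 × 0.141 = 0.28
- n = 200: 1.966 × 0.100 = 0.20

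**Step 2: the same for a binary factor such as shock.** Pearson chi-square, no correction, with an assumed 10% in one group.

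- 30 pairs, 3 v 9 patients (10% v 30%): χ² = 60 × (3×21 − 9×27)² / (12×48×30×30) = 3.75, P = 0.053
- 50 pairs, 5 v 12 (10% v 24%): χ² = 100 × (5×38 − 12×45)² / (17×83×50×50) = 3.47, P = 0.062
- 100 pairs, 10 v 19 (10% v 19%): χ² = 200 × (10×81 − 19×90)² / (29×171×100×100) = 3.27, P = 0.071

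All three pass.

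**Step 3: chance that one test flags a true difference of 0.3 SD.** Normal approximation, Φ(0.3/√(2/n) − 1.96).

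- n = 30: Φ(−0.80) = 21%
- n = 50: Φ(−0.46) = 32%
- n = 100: Φ(0.16) = 56%
- n = 200: Φ(1.04) = 85%

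**Step 4: the opposite error.** If all 15 true differences were zero and the tests independent, the chance of at least one P < 0.05 is 1 − 0.95¹⁵ = 54%. Correlated variables and the matching itself would lower this, but the direction stands: a well-balanced match can miss the stated result by chance.

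**Step 5: where residual imbalance can go.** Compare the list in item 3 with the list in item 4.

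- On both lists (11): age, sex, tumor size, tumor number, MVI, cirrhosis, portal hypertension, hemorrhagic shock, hemoglobin, AFP, AST.
- Matched on but not on the Cox list (4): red blood cell, transfusion, albumin, total bilirubin.
- On the Cox list but not matched on, apart from treatment (4): distant metastasis, platelet, sorafenib, Child-Pugh grade.

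The log-rank test adjusts for none of these. The Cox model can adjust for the first group but not for the second, except for the part of albumin and bilirubin that Child-Pugh grade captures.

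**The case against.** Four objections have weight.

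**The Cox model already protects much of the answer.** Item 4 asks whether treatment is an independent factor, and the Cox model addresses that. Its list covers tumor burden, vascular invasion, cirrhosis, portal hypertension, shock and Child-Pugh grade. This stands. A reader might infer that imbalance lies behind the whole surgery answer; the SAP does not support that. What remains exposed is the log-rank comparison and the four unlisted variables. The SAP also does not say how variables enter the Cox model, so adjustment for the 11 is possible rather than assured.

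**A small match does not pass automatically.** This also stands. Suppose one of 15 variables has a true difference of 0.5 SD and the tests are independent. That variable passes its own test 51% of the time at 30 pairs, and all 15 pass 0.51 × 0.95¹⁴ ≈ 25% of the time. Correlation between variables would raise this, but not to certainty.

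**Item 3 words an expected result, not an acceptance rule.** True: no decision is attached to it. But it stands where a balance standard belongs, and no other is given. A reader might also infer that it rewards a smaller match over a better one. That goes too far, because a tighter caliper also brings propensity scores closer together.

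**A strict limit of 0.1 would misfire in small matches.** With no true difference and random allocation, the standardized difference has standard error about √(2/n), so it falls within 0.1 only about 30%, 38% and 52% of the time at 30, 50 and 100 pairs. Matching does better than random allocation, but a pass-or-fail limit on every variable would often fail, and repeated refitting of the propensity model would invite respecification. The limit should therefore trigger a set adjustment, not another round of matching.

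**Conclusion.** The point holds in a limited form. Non-significance is the only standard of balance in the SAP, it is stated before the data are seen, and what it tolerates depends on the number of pairs. The tolerated difference runs from about 0.52 at 30 pairs to 0.20 at 200. These sizes are assumptions; the SAP gives no reason to expect a small match, and with many pairs the problem shrinks without vanishing. To flag a true difference of 0.20 with 80% power, a test would need 2 × (1.96 + 0.84)² / 0.20² ≈ 393 patients per group.

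The harm falls mainly on the matched log-rank comparison. In the adjusted analysis it is confined, among the matching variables, to the four not on the Cox list, provided that the other 11 are in fact entered. The SAP does not show that large imbalance will occur or that the adjusted treatment effect is wrong. The change is worth making because it is cheap and lets the reader judge the match directly.

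**What to change.** - Reword item 3 so that balance is reported as found.
- Report absolute standardized differences before and after matching for all matching variables and for distant metastasis, platelet and Child-Pugh grade from item 4. Leave out treatment itself, and sorafenib, whose timing relative to surgery is not stated.
- Judge them against one limit fixed in advance, for example 0.1 (a convention, not a figure from the SAP). Keep P values as description only.
- State in advance that any variable above the limit is added to the matched Cox model for treatment, including the four not now listed, with no refitting loop.
- State that this adjusted estimate, not the log-rank test, carries the conclusion on surgery.

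The cost is SAP wording, one extra table column from data already held, and possibly a few more Cox terms, which a small match may support poorly. The report may also have to show residual imbalance that P values would have left unseen.

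### The propensity score in item 3 leaves out distant metastasis, so the unadjusted survival comparison after matching is open to confounding in favour of surgery

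*SAP*

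**What the plan says.** Item 3 gives the matching variables: "The variables included in PSM are: age, sex, tumor size, tumor number, MVI, cirrhosis, portal hypertension, hemorrhagic shock, hemoglobin", then RBC, transfusion, AFP, AST, albumin and total bilirubin. It anticipates that "there is no significance for patients' characteristics after PSM" and gives no separate list for that comparison.

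The comparison list in item 1 ends with "albumin, total bilirubin, Barcelona Clinic Liver Cancer (BCLC) stage, sorafenib, 30-day mortality". It contains an overall stage but does not name distant metastasis.

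The overall-survival lists in items 2 and 4 are the same. The relevant part of item 2 reads "treatment, hemorrhagic shock, distant metastasis, AST, AFP, platelet, hemoglobin, sorafenib, Child-Pugh grade", and that of item 4 reads "treatment, hemorrhagic shock, distant metastasis, AST, AFP, platelet, hemoglobin, Sorafenib, Child-Pugh grade".

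The method after matching is "univariate analysis was performed using the Kaplan-Meier method compared by the log-rank test; multivariate analysis was performed using the" Cox model, and the question to be answered is whether "surgery or non-surgical treatment is (or not) an independent risk factor of overall survival".

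**The concern.** A propensity score should contain the pre-treatment variables that affect both the choice of treatment and the outcome. By putting distant metastasis in both survival analyses, the SAP treats it as a possible predictor of survival. That it also bears on whether hepatectomy is offered is a clinical judgement and not a statement in the SAP, but it is a plausible one. A variable of that kind left out of the score can stay unbalanced however tight the caliper.

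Readers usually take survival curves from a matched cohort as the balanced comparison. Here the log-rank test for treatment has no protection beyond the matching. If matched non-surgical patients have metastasis more often, surgery looks better even when it has no effect. The tables as listed would show this at most indirectly, through BCLC stage.

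**Working it through.** **1. Comparing the lists.** Counting each comma-separated entry gives 21 in item 1, 16 in items 2 and 4, and 15 in the propensity score. If RBC and transfusion are really one entry, item 1 and the score each drop by one and nothing else changes.

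| Variable | Item 1 comparison | Items 2 and 4 (OS) | Item 3 score |
|---|---|---|---|
| Distant metastasis | no | yes | no |
| BCLC stage | yes | no | no |
| Child-Pugh grade | yes | yes | no |
| Platelet | no | yes | no |
| Sorafenib | yes | yes | no |
| Tumor size, tumor number, MVI, AFP | yes | yes | yes |

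Apart from treatment itself, the survival variables missing from the score are distant metastasis, platelet, sorafenib and Child-Pugh grade. Only metastasis and platelet are also missing from item 1.

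**2. Size of the bias.** The SAP has no figure to reproduce: it states no sample size, event count or prevalence. The only input taken from it is the two-sided 0.05 level. Everything else below is assumed:

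- 15% of all patients have metastasis and 40% have surgery.
- Matching is exact and 1:1 on a single tumor-burden score that stands in for size, number, MVI and AFP.
- The odds ratio per SD of that score is 1.65, 2.7 or 4.5 for metastasis and 0.50 for surgery.
- The odds ratio of surgery given metastasis is 0.10 (scenarios A to C) or 0.33 (D to F).
- Survival is exponential with a median of 12 months without metastasis and a cut-off at 36 months. The true treatment hazard ratio is 1.

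Metastasis, surgical vs non-surgical:

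| Scenario | Before matching | After matching | Share of gap removed |
|---|---|---|---|
| A | 2.5 vs 23.3% | 2.6 vs 21.1% | 1 − 18.5/20.8 = 11% |
| B | 2.0 vs 23.7% | 2.2 vs 17.3% | 1 − 15.1/21.7 = 30% |
| C | 1.6 vs 23.9% | 1.9 vs 13.9% | 1 − 12.0/22.3 = 46% |
| D | 6.5 vs 20.7% | 6.8 vs 18.0% | 1 − 11.2/14.2 = 21% |
| E | 5.3 vs 21.5% | 5.9 vs 15.2% | 1 − 9.3/16.2 = 43% |
| F | 4.4 vs 22.0% | 5.1 vs 12.7% | 1 − 7.6/17.6 = 57% |

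The tumor-burden variables therefore give only partial cover.

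**3. Effect on the unadjusted comparison.** At time zero the false hazard ratio is (1 + p_s(h − 1)) / (1 + p_n(h − 1)). Here p_s and p_n are the proportions with metastasis in the matched surgical and non-surgical groups, and h is the hazard ratio for metastasis. Scenario A with h = 2 gives 1.026/1.211 = 0.85, and scenario F gives 1.051/1.127 = 0.93. The ratio moves toward 1 over follow-up because patients with metastasis die earlier. The average over 36 months is therefore milder and was obtained by simulation: 400,000 per group for the hazard ratio, and 10,000 replicates of 100 per group for the log-rank test.

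| Scenario | Unadjusted HR, h = 2 | Log-rank falsely favours surgery, h = 2 | Unadjusted HR, h = 3 | Log-rank falsely favours surgery, h = 3 |
|---|---|---|---|---|
| A | 0.898 | 10.7% | 0.867 | 15.9% |
| B | 0.917 | 9.1% | 0.894 | 12.4% |
| C | 0.932 | 6.9% | 0.909 | 9.3% |
| D | 0.941 | 6.7% | 0.917 | 8.2% |
| E | 0.951 | 6.2% | 0.927 | 6.7% |
| F | 0.960 | 5.0% | 0.942 | 6.3% |

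The nominal rate in that direction is 2.5%. From the mildest to the strongest scenario the false rate is 3.9 to 10.7% with 50 per group and 5.4 to 27.1% with 200 per group (6,000 replicates). A larger cohort makes the problem worse.

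**4. With metastasis in the Cox model.** The treatment hazard ratio is 0.996 to 1.006 and the same error is 1.8 to 3.0% (3,000 replicates). If p_s = p_n, the formula in step 3 gives exactly 1 for any h.

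**The case against.** The strongest reply is that item 4 already deals with this. Its question concerns an independent risk factor, which the Cox model answers, and metastasis is on that model's list. Matching on some covariates and regressing on the others is accepted practice, and the log-rank test is only the univariate step applied to every variable. This largely stands, and it is why the harm is confined mainly to the unadjusted comparison. It does not remove the point. The SAP does not say that the Cox result takes precedence, or that metastasis will be kept in the model.

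The other objections carry less weight:

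- **BCLC stage.** The item 3 table may repeat the item 1 variables, so an imbalance in spread could show through BCLC stage. That is possible, but it would be indirect, and BCLC stage is not matched on.
- **Timing.** The SAP does not say when metastasis is recorded. If it was found after the treatment decision, it does not belong in the score. This stands as a condition on the fix.
- **Platelet.** The list comparison alone applies equally to platelet. True; metastasis is singled out because it is the more plausible driver of both the offer of surgery and survival.
- **Assumed inputs.** No scenario has selection by metastasis near nil, where the bias would vanish. The figures show direction and a possible range, not an estimate.

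**Conclusion.** The point holds. Item 3 leaves out of the score, and names in no comparison table, a variable that the SAP itself analyses as a possible predictor of survival. The post-matching Kaplan-Meier curves and log-rank test for treatment are therefore open to confounding, most plausibly in favour of surgery.

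Under the assumptions shown the bias is modest. The unadjusted hazard ratio is 0.90 to 0.96 if metastasis doubles the hazard and 0.87 to 0.94 if it triples it. With 100 per group, the false rate in favour of surgery is 5.0 to 10.7% and 6.3 to 15.9% respectively. The actual size cannot be found from the SAP. The Cox estimate is protected provided metastasis stays in the model. The change should be made, but the adjusted treatment result does not fall without it.

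Child-Pugh grade is a secondary case of the same kind. Albumin, total bilirubin, cirrhosis and portal hypertension cover it in part, and no size is claimed for it.

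**What to change.** - **Item 3:** add distant metastasis, as recorded at or before the treatment decision, to the propensity score. Child-Pugh grade can be added at the same time.
- **Items 1 and 3:** name distant metastasis in both comparison tables.
- **Item 4:** state that the Cox estimate with metastasis retained is the main treatment result after matching, and that the log-rank test is descriptive.
- **If metastasis is almost absent among surgical patients:** restrict the matched analysis to patients without it and say that the result applies only to them.
- **If the records cannot date metastasis:** state this as a limitation.

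The cost is SAP wording, for a variable already listed in items 2 and 4. If matching has been run, items 3 and 4 must be rerun. Some pairs may be lost. In the six assumed scenarios the loss is 0.7 to 5.7% of pairs when metastasis is also matched exactly, and 3.5 to 9.9% when patients with metastasis are excluded. It could be larger at the tightest calipers, which go down to 0.01. Restriction also narrows the population to which the result applies.
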